4.4 Enrolment

Potential participants will be identified from theatre bookings or direct contact from surgeons or anaesthetists. After identification investigators will:

- Check medical history to confirm all inclusion criteria are met and no exclusion criteria are met.
- Confirm from both surgeon and anaesthetist that participant may be suitable and seek their approval to approach the family.
- Explain the project to the child's family and obtain written consent.

4.5 Subject withdrawal criteria

4.5.1 Failed regional block with general anaesthesia

If the child is having a general anaesthetic (with sevoflurane) and the local anaesthesia block is inadequate (persistent tachycardia or hypertension), then opioids or nitrous oxide may be given at the discretion of the anaesthetist. Post-operative recovery and apnoea data will still be collected, as will neurodevelopmental data. These children will also be followed up in hospital and with a phone call 5 days postanaesthesia as per study protocol. Subjects will not be replaced.

4.5.2 Voluntary withdrawal

Families may withdraw from the study at any stage. If they withdraw, data collected up to that point will still be used for analysis unless the family requests that it is not used. Subjects will not be replaced.

4.5.3 Cancellation of surgery

If the surgery is cancelled after randomisation and not rescheduled, or cancelled and rescheduled greater than 48 hours after randomisation, then the reason for cancellation must be noted and the case is treated as a protocol violation. The child is not replaced. If the child has a hernia repair after 48 hours, the child should receive anaesthesia at the anaesthetist's discretion. Anaesthetic, apnoea and recovery data may be collected if possible. Note that as per other violations, the child should receive two and five year developmental assessment as per protocol. If the child receives surgery for hernia repair 48 hours or more after initial randomisation then they cannot be randomised again in the trial for that later surgery.

Note surgery may be *delayed for up to 48 hours* and the child retains their position in the study with same study group and study number (provided they continue to meet inclusion criteria).

If before anaesthesia and after randomisation a decision is made by surgeon or anaesthetist that the child is no longer suitable for the study for whatever reason (apart from cancelled surgery or withdrawn consent) and the child does not receive their allocated anaesthesia protocol, then the case should be treated as a protocol violation and data collected as possible. The child should receive the same post-anaesthesia apnoea data collection and developmental follow-up as per protocol. Note that if treating staff consider that it is in the child's best interests they always have the opportunity to not follow the protocol, but only the parents can withdraw the child completely from the trial.

5. TREATMENT

5.1 Treatment groups: There are two groups

5.1.1 *General anaesthesia group*: Sevoflurane for induction and maintenance of anaesthesia plus nerve blockade with caudal or ilioinguinal bupivacaine or levobupivacaine

5.1.2 *Awake regional group*: No general anaesthetic agent and one of the following blocks:

- a) Spinal block alone
- b) Spinal and caudal block
- c) Spinal and ilioinguinal block
- d) Caudal block alone.

Note: If two blocks are used, the anaesthetist may chose to give one on completion of surgery.

5.2 Performing nerve block

5.2.1 Agent: All blocks will be with the local anaesthetic agent bupivacaine or levobupivacaine.

5.2.2 Choice of nerve block: Within each treatment group the choice of nerve block is at the discretion of the anaesthetist.

5.2.3 Experience of doctor performing nerve block

An essential component of the trial is a high success rate for regional anaesthesia. At each site awake spinal and caudal may be performed only by anaesthetists with an established high rate of success for the block (>90%). This anaesthetist may be called just to provide the block for the treating anaesthetist.

5.2.4 Asepsis: An aseptic technique is required for all blocks. This includes:

- Hands washed and sterile gloves worn
- Surgical masks to be worn
- Skin preparation with an antiseptic
- Area covered with sterile drapes

5.3 Details of General Anaesthesia group treatment protocol

5.3.1 Pre-operative management:

- Pre-operative fasting in accordance with institutional guidelines
- Premedication with oral paracetamol (acetaminophen) 20mg/kg [optional]

5.3.2 Induction:

- Sevoflurane up to 8% induction in air/oxygen mix
- No nitrous oxide
- Circuit and fresh gas flow at discretion of anaesthetist
- Oxygen concentration at discretion of anaesthetist
- IV insertion before or after induction

5.3.3 Maintenance:

- Airway maintenance: Endo-tracheal intubation, laryngeal mask or face mask only with or without an oral Guedel airway.
- A non-depolarizing neuromuscular blocking agent (NDNMB) may be used to facilitate endo-tracheal intubation.
- Analgesia with caudal local anaesthesia blockade with bupivacaine or levobupivacaine or ilioinguinal nerve local anaesthesia up to a maximum dose of 2.5mg/kg bupivacaine or levobupivacaine
- Maintenance with sevoflurane in an air/oxygen mix. Sevoflurane concentration at discretion of anaesthetist. No nitrous oxide.
- Mechanical or spontaneous ventilation to maintain end tidal CO₂ between 35 and 45 mmHg. Fresh gas flows and circuit at discretion of anaesthetist.
- Oxygen concentration at discretion of anaesthetist to maintain arterial oxygen saturation > 95%
- Reversal with neostigmine 0.05 mg/kg and atropine 0.02 mg/kg if NDNMB used.
- During anaesthesia administer Ringer's lactate solution at 4ml/kg/hr
- Warming in accordance with institutional practice

5.4 Details of Awake Regional group treatment protocol

5.4.1 Pre-operative management:

- Pre-operative fasting in accordance with institutional guidelines
- Premedication with oral paracetamol (acetaminophen) 20mg/kg [optional]

5.4.2 During anaesthesia:

- IV insertion before or after spinal/caudal, IV fluids ringer's lactate at 4ml/kg/hr
- Oral sucrose for sedation/analgesia. No other sedation
- No volatile anaesthetic agents may be given at any stage
- Warming in accordance with institutional practice
- Oxygen by face mask or blow by at discretion of anaesthetist to maintain arterial oxygen saturation > 95%

5.4.3 Nerve blockade

5.4.3.1 Spinal anaesthesia nerve blockade:

- 25 gauge needle lumbar puncture at L2-3 or L3-4,
- Dose of bupivacaine or levobupivacaine up to 0.2 ml/kg 0.5% bupivacaine or levobupivacaine (minimum volume of 0.5ml)
- Child may be in lateral or sitting position

5.4.3.2 Caudal blockade

- Dose of bupivacaine or levobupivacaine up to 2.5 mg/kg bupivacaine or levobupivacaine, concentration at discretion of anaesthetist
- Via needle or cannula

5.5 Post-operative management for both groups:

• Paracetamol (acetaminophen) 20mg/kg oral or intravenous at discretion of anaesthetist if not given pre-operatively

- IV fluids Ringer's lactate @ 4ml/kg/hr until feeding,
- Temperature maintenance as per institutional practice
- Oxygen by face mask or blow by at discretion of anaesthetist or nurse in PACU to maintain arterial oxygen saturation > 95%

5.6 Treatments not permitted during anaesthesia

- Opioids may not be given.
- Benzodiazepines, nitrous oxide, ketamine and clonidine may not be given.
- No drugs apart from bupivacaine or levobupivacaine may be added to any nerve block

5.7 Triggers to abandon awake regional and administer general anaesthesia

If there is a failed awake regional on clinical assessment then the infant is given a general anaesthetic with sevoflurane alone and continues in the study. In this situation the airway management is at the discretion of the anaesthetist. Regional failure may be due to movement impeding surgery or a vigorous crying child that cannot be comforted.

Note: If there is total failure of a spinal then the spinal may be attempted again with another 1mg/kg bupivacaine or levobupivacaine. Total failure is defined as follows: after 5 minutes the infant continuing to vigorously spontaneously move both their legs with no evidence of motor block and withdrawing both their legs after gentle pinch to either thigh. Any suggestion of only partial failure and the child should not receive another spinal attempt. Total dose of bupivacaine or levobupivacaine for entire case may not exceed 2.5 mg/kg.

5.8 Rescue treatments

5.8.1 Blood pressure

Intra-operative and PACU; if blood pressure > 20% below baseline give IV bolus of 20 ml/kg Ringers lactate solution. Vasoactive drugs if deemed necessary by anaesthetist. Note baseline blood pressure defined as blood pressure in a comforted non-distressed child.

5.8.2 Blood glucose

Give intravenous glucose bolus 5ml/kg 10% dextrose for hypoglycaemia (Blood sugar level <3.0 mmol/L)

5.8.3 Hypoxia

Hypoxia to be managed with oxygen via mask and/or intubation in regional group and increasing FiO_2 in GA group as deemed necessary by anaesthetist.

5.9 Follow-up

For success this trial requires a high rate of retention for the 2 and 5 year assessment. Therefore a family will be excluded if geographic or extreme social circumstances make follow up difficult. Families will receive a phone call one week after the hernia repair and then cards on the child's birthdays and regular newsletters. This will be co-ordinated from Melbourne in terms of study number only and date of surgery by a prompt alerting each local site to send out a card.

6. OUTCOME

6.1 Primary outcome

The primary outcome will be the WPPSI-III Full Scale IQ score at 5 years corrected age.

6. 2 Secondary outcomes

Secondary outcomes fall into four areas:

- 1) Other measures of neurodevelopmental outcome
- 2) Incidence of apnoea
- 3) Other outcomes relating to anaesthesia group
- 4) Incidental outcomes not related to choice of anaesthesia

6.2.1 Other measures of neurodevelopmental outcome

6.2.1.1 Neurodevelopmental secondary outcomes at 2 years:

- Cognitive, motor and language scales of the Bayley Scales of Infant Development III [Bayley 2005].
- A paediatric assessment including a neurological examination to determine the presence of cerebral palsy will be conducted by a paediatrician blinded to the type of anaesthetic used.
- Data regarding visual and hearing acuity will be collected, or where not previously conducted, visual and audiology assessments will be arranged.
- Some sites will perform the experimental Delayed Alternation and Spatial Reversal tasks (Espy)

6.2.1.2 School age developmental outcome at 5 years:

- A paediatric assessment as per 2 years.
- General intellectual ability, verbal, visuo-spatial and processing speed skills are incorporated into the Wechsler Preschool and Primary Scale of Intelligence - Third Edition (WPPSI-III) The primary outcome is the full scale, while subscales will be computed as secondary outcomes.
- Auditory and visual attention will be assessed using the NEPSY tasks.
- The behaviour features of executive dysfunction will be assessed via the Behavioural Rating of Executive Function (BRIEF).

6.2.2 Apnoea

Apnoea will be defined in terms of changes in recorded vital signs and need for intervention. The timing of the apnoea will also be early or late.

6.2.2.1 Significant apnoea by vital signs

A significant apnoea will be defined as a pause in breathing of greater than 15 seconds or a pause greater than 10 seconds if associated with oxygen saturation <80% or bradycardia (20% fall in heart rate).

6.2.2.2 Significant apnoea by intervention

Any intervention for apnoea will be recorded as frequency, time and nature of intervention. Types of intervention recorded will include need for stimulation, assisted ventilation, CPAP, endo-tracheal intubation administration of a methylxanthine stimulant, delay in discharge home due to apnoea or discharge from hospital with a home apnoea monitor.

6.2.2.3 Early apnoea

Any significant apnoea in the PACU or the first 30 minutes of the NICU if PACU is bypassed or in the operating room after completion of surgery, discontinuation of general anaesthesia and removal of laryngeal mask or endo-tracheal tube.

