3.5.6.1 Anaesthesia details. Regional group only

Seniority of anaesthetist Times for anaesthesia blocks and surgery Blocks used and details of block technique including position of child, dose and concentration of bupivacaine or levobupivacaine, number of needle passes, presence of blood in needle and flow of CSF through needle Distress of child and SpO₂ and HR during the block Volume and type of fluid given in theatre Blood glucose and haemoglobin Details of any rescue therapy for low glucose, hypotension or hypoxia Efficacy of block and activity of child during the procedure Details of any respiratory support or apnoea during procedure HR, NIBP, SpO₂ and activity of child every 5 minutes during surgery

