3.5.6.2 Anaesthesia details. General group only

Seniority of anaesthetist Times for anaesthesia induction and times for blocks and surgery Blocks used and details of block technique including dose and concentration of bupivacaine or levobupivacaine, number of needle passes, presence of blood in needle and flow of CSF through needle Details of anaesthesia induction Details of airway management and use of any NDNMB Volume and type of fluid given in theatre Blood glucose and haemoglobin Details of any rescue therapy for low glucose, hypotension or hypoxia Efficacy of blocks Details of awakening, airway removal and reversal of any NDNMB Details of any respiratory complications or apnoea during awakening or after airway removed. HR, NIBP, Inspiratory oxygen, SpO₂ and End tidal CO₂ and sevoflurane concentrations every 5 minutes during surgery

The total dose of sevoflurane will be calculated as concentration*hours dose equivalent

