3.5.8 Post anaesthesia care unit data

In PACU (or during the first 30 minutes on the ward if PACU is bypassed) the following adapt will be collected:

Details of monitoring for apnoea Drugs given Number of significant apnoeas Details of any intervention for apnoea or respiratory support needed HR, NIBP, SpO₂ every 5 minutes during PACU stay and lowest SpO₂ FALCC scores and details of any analgesia Presence of stridor Time to first feed Sunken fontanel, any persistent CSF leak

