6.2.2.4 Late apnoea

Any documented significant apnoea occurring in NICU or other hospital ward within 24 hours of completion of surgery, excluding early apnoeas.

6.2.3 Other outcomes relating to anaesthesia group:

- Success rate of nerve block
- Time taken for nerve block
- Behaviour of child during nerve block, during surgery and in PACU
- Time to first feeding

6.2.4. Incidental outcomes not related to choice of anaesthesia:

• Incidence of hernia recurrence at 2 years will be recorded. If the repair was unilateral the incidence of contralateral occurrence will be noted.

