7. SAFETY

7.1 Monitoring during anaesthesia and in PACU

During all nerve blockade there will be ECG, NIBP and pulse oximetry monitoring. During anaesthesia for both groups there will be ECG, NIBP, temperature and pulse oximetry. In the general anaesthesia group there will also be agent analysis and expired CO₂. Blood glucose and haemoglobin will be measured during anaesthesia. In PACU there will be monitoring of oxygen saturation, NIBP, temperature, respiratory rate and heart rate.

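### As written, the operating-room part of the early-apnoea definition cannot be met by awake-regional or face-mask-only infants, and its PACU-bypass window names only the NICU while the data list says ward

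*Protocol*

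**What the plan says.** Section 6.2.2.3 defines early apnoea by place and time. One limb covers recovery: "Any significant apnoea in the PACU or the first 30 minutes of the NICU if PACU is bypassed". The other covers theatre: "in the operating room after completion of surgery, discontinuation of general anaesthesia and removal of laryngeal mask or endo-tracheal tube".

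Section 6.2.2.4 defines late apnoea as "Any documented significant apnoea occurring in NICU or other hospital ward within 24 hours of completion of surgery, excluding early apnoeas".

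The theatre data items differ by arm. For the regional group, 3.5.6.1 lists "Details of any respiratory support or apnoea during procedure". For the general group, 3.5.6.2 lists "Details of any respiratory complications or apnoea during awakening or after airway removed". The next collection point is 3.5.8, which covers PACU or "during the first 30 minutes on the ward if PACU is bypassed".

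Section 5.1.2 gives the awake regional group no general anaesthetic agent. Section 5.3.3 lets the airway in the general group be held by tube, "laryngeal mask or face mask only with or without an oral Guedel airway".

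**The concern.** Early apnoea supplies two of the four apnoea outcomes in 8.2.2 (by vital signs and by intervention). Describing apnoea after both techniques is a stated secondary aim (2.2.2), and the DMC looks at apnoea rates by group (7.2). These uses need a window that opens in the same way whichever technique the infant received.

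The theatre limb is instead tied to two events that belong to general anaesthesia with an airway device. An infant who had neither cannot satisfy it, so whether an identical event counts depends on the arm and, within the general arm, on the airway used.

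The recovery limb has a different fault. It names a narrower place than the data list that feeds it, so an event can be collected as immediate recovery data and then analysed as late.

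**Working it through.** No plan figure needs reproducing. The protocol states no apnoea rate and no sample size for apnoea; the 598 and 660 in 8.3 belong to the IQ outcome. The check is a reading of the definitions against the treatment and data sections.

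**Step 1: the theatre limb.** Take a 20-second breathing pause in theatre after surgery has ended. It passes the 15-second threshold in 6.2.2.1. Apply the three joined conditions (surgery complete, general anaesthetic stopped, laryngeal mask or tube removed):

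| Infant | Surgery complete | Anaesthetic stopped | Mask or tube removed | Early? |
|---|---|---|---|---|
| General, tube or laryngeal mask, now out | yes | yes | yes | yes |
| General, face mask only (5.3.3) | yes | yes | none was used | no |
| Awake regional (5.1.2) | yes | none was given | none was used | no |
| Regional converted to sevoflurane (5.7), tube or laryngeal mask, now out | yes | yes | yes | yes |

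**Step 2: does another category catch the missed events?** Late apnoea under 6.2.2.4 is confined to the NICU or another ward. The event is in theatre, so for the second and third infants it is neither early nor late.

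**Step 3: does the interval exist in regional infants?** Yes. The note to 5.1.2 allows one of two blocks to be given when surgery has finished, so a regional infant may still be in theatre under active care at that point.

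**Step 4: would the data allow repair at analysis?** Only in part.
- The general list names awakening and the time after airway removal. The regional list names the procedure. The next list starts in PACU. No regional item plainly covers the minutes between the end of surgery and leaving theatre.
- Section 3.6 specifies continuous recording for PACU, not for theatre.
- Section 6.2.2.2 does record every intervention for apnoea with its time, without limiting this by arm or place. Theatre interventions in regional infants should therefore be on record, and the outcome based on intervention is partly protected. Pauses that meet the vital-signs rule without any intervention are not.

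**Step 5: the bypass window.** Take an apnoea 10 minutes after direct transfer from theatre to an ordinary ward.
- 3.5.8 collects it with the PACU data, because it falls in the first 30 minutes on the ward.
- 6.2.2.3 does not count it as early, because the bypass window there is the NICU, which the abbreviation list defines as the neonatal intensive care or neonatal unit.
- 6.2.2.4 therefore classes it as late.
- The same event 10 minutes after direct transfer to the NICU is early.

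**Step 6: direction and size.** Steps 1 and 4 point to under-counting in the regional arm. Two features shrink the contrast: face-mask infants in the general arm are also missed, and converted regional infants with a tube or laryngeal mask are counted. Sizing it would need the share of early apnoeas that occur in theatre, the share of general-arm infants managed by face mask, and how each site reads the clause. The protocol gives none of these.

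**The case against.** The strongest reply is that this is loose drafting. A sensible reader applies each condition only where it exists, so that the window opens at the end of surgery for a regional infant and at the end of the anaesthetic for a face-mask infant. Nothing suggests that face-mask infants were meant to be excluded. That is fair as to intent. But the text does not say so, although the recovery limb of the same sentence carries an explicit conditional for a bypassed PACU. The charitable reading also leaves the regional data list without an item that clearly covers the interval. The lists in 3.5.6 are summaries and the case report forms are not shown, so the gap in capture is probable, not certain.

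Three stronger readings are tempting, and the protocol does not support them.
- *Respiratory monitoring is lopsided in this window.* Section 7.1 does say "In the general anaesthesia group there will also be agent analysis" and adds expired CO2, but it places this during anaesthesia, which has ended when the theatre limb opens. For that interval it shows no difference between the arms.
- *The error favours what unblinded assessors already believe.* Apnoea assessment is unblinded (3.3), but section 11 argues equipoise and says any apnoea advantage of regional anaesthesia may be smaller with newer agents. A shared prior belief is not documented.
- *A spurious risk ratio can be calculated.* Any such figure would be fixed entirely by an assumed share of events in theatre, with full loss in one arm and full capture in the other.

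It is also true that the apnoea aim is descriptive, with no apnoea hypothesis or margin, and that the NICU and ward mismatch applies to both arms alike. The mismatch is a separate inconsistency and no evidence of bias between arms.

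**Conclusion.** The point stands as a fault in a secondary-outcome definition. Followed exactly, 6.2.2.3 counts a theatre apnoea after surgery in general-arm infants who had a laryngeal mask or tube, and leaves the same event unclassified in awake-regional and face-mask-only infants. The likely direction is under-counting in the regional arm, mainly for early apnoea by vital signs; early apnoea by intervention is partly protected by 6.2.2.2. This rests on the literal wording and on the data lists reflecting what the forms ask. The size cannot be found from the protocol.

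The NICU and ward mismatch is a plain contradiction that moves events between early and late. It does not depend on how the theatre limb is read.

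The IQ primary outcome and its sample size are unaffected. Both faults should be corrected, because an event that was never recorded cannot be recovered at analysis.

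**What to change.** 1. Reword the theatre limb of 6.2.2.3 so that the window exists for every infant: *from completion of surgery and, where used, after general anaesthesia has been discontinued and any laryngeal mask or tube removed, until leaving theatre*. For a face-mask infant the window then opens when surgery is complete and the anaesthetic has been stopped, and no judgement is needed about when a face mask counts as removed.
2. Add one item to the regional list in 3.5.6.1: apnoea or respiratory support from completion of surgery to leaving theatre.
3. Change the bypass clause in 6.2.2.3 to *NICU or ward*, to match 3.5.8.

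The cost is one reworded definition and one extra data item. No treatment or clinical rule changes.
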